4.3 Study Enrollment Procedures

This study will recruit 100 individuals assuming about 20% missing data due to unusable imaging data and dropouts as has been previously demonstrated (34). The ability to be hypnotized is a stable and measurable trait that can be pre-screened and quantified (94, 105, 106). A member of the study team that has been trained by [name] will select subjects prior to randomization according to their ability to be hypnotized prior to the MRI visits using the Hypnotic Induction Profile (HIP). Hypnotizability is correlated about 0.6 with the ability to experience hypnotic pain relief (107). Participants will be selected those with low-moderate hypnotizability (scores of 0-8 on the HIP from a range 0-10) (94) in order to prevent a ceiling effect (see Appendix IV for the manual describing the HIP). IRB approval has been obtained to request that treating doctors at Stanford Hospital and Clinics send an invitation to patients they are seeing with Fibromyalgia Syndrome to participate in the study. Recruitment efforts will concentrate on physicians at the Stanford Center for Integrative Medicine, the Stanford Pain Clinic, the Stanford General Neurology Clinic, the Stanford Immunology and Rheumatology Clinic and the Stanford Chronic Fatigue Clinic.

The *NCCIH Site Screening and Enrollment Log* will be utilized to record the consent and screening of all subjects and the outcome of each screening. This log will provide a comprehensive list of all subjects who were screened for eligibility if the information is not maintained electronically. Subjects will be recorded as they are consented, to ensure completeness and accuracy of the data. All subjects will be included who were consented and screened, including screen failures. This log will not contain identifying information. Subjects will be tracked separately on logs in a coded list with a key. Each page will be numbered and maintained in this log in the *Essential Documents Binder*, behind the *Screening/Enrollment Log* tab. Pages will be stored in reverse chronological order, with the newest pages of the log placed at the front of the section. At the conclusion of the study, the final page of the log will be identified by checking the box in the footer.

The participant will be consented in the sequence defined by the NCCIH. The consent process will start with an introductory paragraph that describes the study. This will be followed by a description of the purpose of the research. Next, the procedures will be described and the time duration of these procedures and as well as the total study duration. The participant will be notified of the discomforts and risks along with the potential benefits of participation in this study. The participant will then receive a statement of confidentiality. The participant will be notified that there are no costs for participation in this study as well as being notified that there is compensation for participation in the study. The participant will be made aware of the research funding source. The participant will be given information regarding the fact that their participation is voluntary. The participant will then be given the contact information for questions or concerns. Finally, the participant will be asked for their signature in order to consent and give permission to be in the research study.

The consent includes a statement that involves a description of the research. The consent includes an explanation of the purposes of the research. The expected duration of the individual's participation is listed in the text of the consent. A description of the procedures to be followed is also included in the text of the consent. Identification of the experimental procedures is listed in the consent. A description of any reasonably foreseeable risks or discomforts to the participant is stated in the consent. A description of the benefits to the participant or to others, which may be reasonably expected from the research study is listed in the consent. A disclosure of appropriate alternative procedures or courses of treatment if any that might be advantageous to the patient is listed in the consent. A statement describing the extent, if any, to which confidentiality of records identifying the patient will be maintained is listed in the consent. An explanation of who to contact for answers to pertinent questions about the research and participant's rights and whom to contact in the event of a research related injury to the participant is listed in the consent. A statement that the research is voluntary, refusal to participate will involve no penalty or loss of benefits to which the individual is otherwise entitled and the individual may discontinue participation at any time without penalty or loss of benefits, to which he/she is otherwise entitled is listed. A description of the clinical trial will be made available on www.ClinicalTrials.gov as required by US Law. The participants will be made aware of this and that this listing will not in any way identify them.

5. STUDY INTERVENTIONS

5.1 Interventions, Administration, and Duration

The transcranial magnetic stimulation (TMS) device (MagPro, Medtronic Functional Diagnostics, Skovlunde, Denmark) utilized is a computerized electromechanical instrument that produces and delivers brief duration, rapidly alternating (pulsed) magnetic fields to induce electrical currents in localized regions of the cerebral cortex. Since the TMS device produces a time varying magnetic field, its intended effect derives fundamentally from Faraday's Law, which asserts that a time-varying magnetic field produces an electrical current in an adjacent conductive substance. During TMS application, the conductive substance of interest is the brain, in particular the region of the cortex that lies beneath the stimulation coil.

The electric current induced in the targeted region of the cortex travels in a path orthogonal to the direction of the alternating magnetic field with the point of maximum field strength and greatest current located directly beneath the center of the coil, which is the component that rests against the patient's head and transmits magnetic pulses to the patient's brain. The induced current is tangential to the scalp at the cortical surface, and diminishes in magnitude with increasing depth. In the area of the motor cortex targeted for motor threshold acquisition, where field strength achieves the stimulation threshold, it is postulated that neuronal depolarization occurs. The peak magnetic field strength achieved with each pulse is approximately 0.5 Tesla.

Although the mechanism of action is unknown, it is hypothesized that a TMS device causes direct neuronal modulation in brain regions immediately adjacent to the magnetic coil, and also results in changes in functional activity and connectivity in areas of the brain that are synaptically connected to the brain regions experiencing direct neuronal modulation. It is thought that these actions may cause various physiologic changes in the brain. TMS is a technique capable of modulating targeted cognitive processes (108, 109). TMS has previously been demonstrated to enhance hypnotizability (26). Traditional rTMS has limited duration of after-effects (26, 110). A new stimulation approach termed continuous theta-burst stimulation (17) has been demonstrated to have an extended duration of after-effects, particularly if administered in a patterned, spaced paradigm (27-30, 79).

Administration: The TMS stimulator (MagPro, Medtronic Functional Diagnostics, Skovlunde, Denmark) will be used to generate repetitive biphasic magnetic pulses. Magnetic pulses will be delivered with a figure-eight-coil (Cool-B65 A/P-Coil). The L-DLPFC will be localized according to previously described procedures where combined functional and structural imaging is utilized to find the area of greatest connectivity with dACC (81). The participant will receive stimulation over the left motor cortex with single pulses in order to determine that individual's motor threshold through measurement of the corresponding muscle twitching of the subject's relaxed abductor pollicis brevis as measured by electromyography (EMG) once and visual inspection once (91). The PEST procedure will be utilized during the MT acquisition portions of the study (90). Once the MT has been determined, the coil will be moved to the neuronavigated L-DLPFC target(81). The handle of the coil will be pointed backwards (45° angle to the sagittal line) and will be fixed to the stimulation arm (30).

Dosing Schedule: A spaced theta-burst technique will be employed that will modulate the neural network node in targeted neural network for the entirety of the scanning session (27-30, 79). Theta burst TMS will be applied over the left dorsolateral prefrontal cortex (L-DLPFC). Two applications of 800 pulses of continuous theta-burst stimulation at 80% of the resting motor threshold will be utilized as this has been demonstrated effective in producing several hours of change in cortical excitability (30) and safe (17). The decision to choose a 15-minute interval is based on the results of the several human experiments using this spaced approach(29, 30) and on long-term depression (LTD) protocols used in animals, where it has been demonstrated that cTBS trains spaced in the order of 10-15 minute intervals generate more persistent LTD (111).

Potential Adverse Events: Repetitive transcranial magnetic stimulation (rTMS) is generally regarded as safe and without any serious or lasting adverse effects (99, 112). A newer form of rTMS, termed continuous theta-burst stimulation (cTBS), is an even safer intervention and is suggested to be minimal risk in children (21-23). Inadvertent induction of a seizure is the most medically significant, potential safety concern. Seizure has only been observed once with cTBS and only in exceedingly high stimulation settings (24, 85). Furthermore, with the adoption and widespread use of recommendations delineating a safe margin for TMS dosing parameters as disseminated in the 1998 TMS consensus safety guideline from the National Institute of Neurological Disorders and Stroke (NINDS), the risk for seizures during rTMS in general is significantly mitigated. This study will comply with NINDS guideline standards for transcranial magnetic stimulation (TMS) (99, 112). It is important to note that there is no evidence in the literature to indicate that a single seizure during TMS makes subsequent seizures more likely in an otherwise non-seizure-prone individual. There are potential consequences of a seizure, regarding employment or insurability in the future. If a subject does experience a seizure related to this investigation, a letter from the PI will note that the seizure was produced under experimental conditions, and there is no reason to expect another seizure in the future.

There is no known risk of seizure with the currently stated parameters (17, 24). In order to have a seizure from inhibitory rTMS (cTBS), one must receive stimulation that is at or greater than 100% of the participant's motor threshold (MT) (24). The MT is reflective of stimulation output necessary to cause a neuronal depolarization (83). Without neuronal depolarization, seizure from rTMS has not been demonstrated to occur. The traditional rTMS parameters have resulted in seizure because these require 120% of the MT (84). cTBS has been demonstrated to modulate the brain with less than 100% motor threshold (17). Only one case of cTBS has resulted in seizure and this case was related to using 100% MT (24, 85). cTBS has been utilized safely in children with no incidence of seizure (21, 22) and has been suggested to be similar risk to single and paired pulse TMS (21), which has been rated as minimal risk for children (23). Inhibitory rTMS (cTBS) will be administered in the Stanford Center for Cognitive and Neurobiological Imaging and outside the scanner. Benzodiazepines will be on hand in the event of seizure and the participant will be immediately transferred to the Emergency Room. Because of the fixed nature of the stimulation dose, there will be no modification to the stimulation parameters. The dose of inhibitory rTMS (cTBS) is personalized for each participant through the use of resting motor threshold acquisition (90).

Hearing Risk: There is the potential risk of alteration in auditory threshold secondary to exposure to rTMS. As a result of the rapid changes in the magnetic field during rTMS administration, the coil produces an audible, high-energy clicking sound, which may be associated with temporary increases in auditory threshold. During previous studies with the rTMS approaches, all subjects were required to use hearing protection at a protection rating of ≥ 30 db. No change in hearing was found with air conduction threshold testing in the two randomized clinical studies when this method of ear protection was used. All participants will be asked to use earplugs for this study.

Other side effects of TMS: Prophylactic use of acetaminophen or ibuprofen will be allowed for subjects reporting sensations at or near the stimulation site, which are uncomfortable or painful. Participants reporting headaches during or following study stimulation session will be encouraged to take acetaminophen or ibuprofen prior to the stimulation session. All subjects will be monitored, and appropriate treatment will be recommended including the possibility of discontinuing the next scanner day. Any other potential side effects will be managed symptomatically with treatment(s) deemed appropriate by the study site Principal Investigator. All symptomatic interventions will be recorded in the subject's case file and, if applicable, adverse event CRF.

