utilize a combined structural and functional targeting approach because the area of the L-DLPFC that is being targeted to modulate is the area that has the highest connectivity with the dACC. It has been demonstrated previously that such an approach can be applied within the L-DLPFC(58). Once the pre-TMS scan session is complete, the images will be exported to the Localite Neuronavigation System (93) so that while the participant is undergoing their motor threshold (MT) elicitation and the neuronavigation targeting is occurring such that the participant's target and dose will be completed in time for the rTMS (cTBS) session.

Stimulation Parameters: 80% of the resting motor threshold (rMT) was chosen as the dose of cTBS as this dose has been demonstrated to be optimal in suppressing the MEP. We will adjust the skull-prefrontal cortex distance to account for any differences in differential volume loss. We will utilize 800 pulses of continuous theta-burst (cTBS) with 30 Hz bursts at 6Hz as this has been demonstrated to be optimal in suppressing the MEP(82). We will apply two stimulation trains of 800 pulses with a 15-minute space in between each train of cTBS as has been previously described(27, 30). This stimulation session will be performed in between the pre- and post- TMS scanner sessions for both scanner session days (total of two stimulation sessions for each participant). The participant will receive cTBS stimulation in the manner described in the manual that is attached to the appendix of this protocol. The handle of the coil will be pointed backwards (45° angle to the sagittal line) and will be fixated in an arm. In order to preserve the blind, the participant will be randomized to the same rTMS (cTBS) condition for both scanner days(86).

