4. SELECTION AND ENROLLMENT OF PARTICIPANTS

4.1 Inclusion Criteria

Participants must meet all of the inclusion criteria to participate in this study.

Inclusion Criteria Include:

1. Fulfill 2010 Fibromyalgia Diagnostic Criteria(1)
2. Age 18-70 years old
3. Right-handed(96)
4. Agree to and able to have at least three fMRI scan sessions as well as rTMS(97) sessions
5. Willingness to suspend use of analgesic drugs or cough suppressants for 24 hours prior to the scans
6. Willingness to suspend use of antidepressant drugs for 2 weeks prior to the scans (6 weeks for fluoxetine)
7. Proficiency in English sufficient to complete questionnaires / follow instructions during fMRI assessments
8. US Citizen or resident able to receive payment legally
9. Low-Moderate Hypnotizability in the Hypnotic Induction Profile (score of 0-8)(98)
10. Normal color vision
11. Not pregnant and if participant is of childbearing potential, must agree to use adequate contraception prior to study and for the duration of study participation.

We will enroll 18-70 year old right-handed(96)*, male and female participants with a confirmed diagnosis of Fibromyalgia Syndrome (FMS)(1), low-moderate hypnotizability (a HIP score from 0-8)(98), no contraindications to rTMS(97) or MRI(89) and no other disease causing pain.

**Right-hand dominant ambidextrous participants are included.*

Required Diagnostics: Individuals will meet gold-standard criteria for FMS. The confirmation of diagnosis involves meeting the gold-standard criteria for the diagnosis of FMS, the American College of Rheumatology Preliminary Diagnostic Criteria for Fibromyalgia(1). Participants will meet criteria within 2 months prior to the date of first scanning session. Individuals will have a normal CBC and inflammatory panel. Participants will have to have labs drawn within 1 year.

Prior Therapy: Participants cannot be taking psychoactive medications (antidepressants, opiates) during the rTMS sessions due to increased risk of seizure(99) and/or manipulation of the participant's cortical excitability(100). We will not require participants to have taken any prior medications/therapies for FMS to be included in this study. Participants will have to have the ability to understand study procedures and to comply with them for the entire length of the study.

Participants cannot have been exposed to TMS in any way prior to enrolling in this study because it will affect blinding(86).

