5.3 Concomitant Interventions

5.3.1 Allowed Interventions

Zaleplon, zolpidem, or zopiclone (1 dose) as needed for significant insomnia during the night prior to the scanner sessions or lorazepam (up to 2 mg) for significant anxiety during the day and night prior to the scanner sessions. These medications may be administered up to the night prior to the stimulation session (until 8:00 PM), but not during the morning of the sessions or at any time during the scanning day (100). The use of alternative hypnotics or anxiolytic compounds requires prior approval from the PIs. Hormonal contraceptives are allowed if the subject has been on a stable dose for at least 3 months. Short-term treatments for headaches, allergies, colds, and flu symptoms will be allowed during the study provided the medications utilized have no established psychotropic effects that would be expected to confound interpretation of study outcome measures. These medications may include non-sedating, over-the-counter, or prescription antihistamines, analgesics and decongestants.

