5.3.3 Prohibited Interventions

Any medication administered for the treatment of any psychiatric or neurologic disorder or any other known CNS active drugs, including herbal, over-the-counter, and homeopathic medications, MAOIs, other antidepressants, antipsychotics, stimulants, opiates, pain medications, and mood stabilizers are prohibited during the day prior to and day of the scanner sessions. Use of zaleplon, zolpidem, zopiclone or lorazepam too close to the time of stimulation or beginning a new regimen of hormonal contraception may lead to excluding the subject from the study.

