Data Collected to Assess Safety During rTMS: Treaters will be monitoring subjects for the potential development of seizures by continuous visual inspection during the course of each stimulation session (especially the more subtle signs and symptoms of frontal lobe seizures), and first responder management in the event of a seizure. The study personnel have immediate (i.e., within minutes) availability of more sophisticated medical support, including access to an emergency room, in the event that a seizure is not a self-limited event, access to antiepileptic medications, and to life support equipment including oxygen, suction, blood pressure monitoring and cardiopulmonary (CPR) equipment.

Seizure and the following are AE's that will be reported at solicited events:

Body System - Preferred Term	Active TMS (N=165) N (%)	Sham TMS (N=158) N (%)
Eye disorders - Eye pain	10 (6.1)	3 (1.9)
Gastrointestinal disorders - Toothache	12 (7.3)	1 (0.6)
General disorders and site administration conditions - Application site discomfort - Application site pain - Facial pain	18 (10.9) 59 (35.8) 11 (6.7)	2 (1.3) 6 (3.8) 5 (3.2)
Musculoskeletal and connective tissue disorders - Muscle twitching	34 (20.6)	5 (3.2)
Skin and subcutaneous tissue disorders - Pain of skin	14 (8.5)	1 (0.6)

Table 2: Adverse events with an incidence in active rTMS at a rate of > 5% and at least 2x sham in the safety exposure study population. These symptoms have occurred only during and not after rTMS administration.

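### The protocol both bars and encourages analgesics around stimulation on scan days, and no analysis rule covers the resulting use in the pain-threshold outcome

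*Combined protocol and SAP*

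**What the plan says.** Four places in the protocol govern analgesics around scan days.

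- Section 4.1 (Inclusion Criteria) requires "Willingness to suspend use of analgesic drugs or cough suppressants for 24 hours prior to the scans".
- Section 5.3.3 (Prohibited Interventions) states that "opiates, pain medications, and mood stabilizers are prohibited during the day prior to and day of the scanner sessions".
- Section 5.1 (Other side effects of TMS) states: "Prophylactic use of acetaminophen or ibuprofen will be allowed for subjects reporting sensations at or near the stimulation site", where these are uncomfortable or painful. Participants with headaches during or after stimulation "will be encouraged to take acetaminophen or ibuprofen prior to the stimulation session".
- Section 5.3.1 (Allowed Interventions) permits short-term treatment of headache and minor illness: "These medications may include non-sedating, over-the-counter, or prescription antihistamines, analgesics and decongestants". The only proviso is that the drug has no psychotropic effect expected to confound the outcomes. There is no exception for scan days and none for an analgesic effect on a pain endpoint.

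On timing, section 3 (Stimulation Parameters) says: "This stimulation session will be performed in between the pre- and post- TMS scanner sessions for both scanner session days". Section 9.7 defines the relevant clinical outcome through change in pain thresholds. Section 9.6.1 has the thermal tests done before rTMS plus hypnotic analgesia and every 5 minutes for 30 minutes afterwards.

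Symptomatic treatment is recorded (section 5.1), and concomitant medications are collected on both scan days (section 6.1). Sections 9.4, 9.6.1 and 9.7 give no rule for analgesic use in the pain analysis. The separate SAP covers only HIP scores and a test of the blind.

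**The concern.** Any dose taken before a stimulation session is taken on a scan day, or shortly before one, and within 24 hours of the post-rTMS scan. Staff who follow section 5.1 therefore breach sections 4.1 and 5.3.3, and staff who follow those sections cannot follow section 5.1.

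The conflict matters statistically because the drug class acts on the quantity being measured. An analgesic taken between the baseline and post-rTMS thermal tests raises the post-rTMS threshold for a reason other than hypnotic analgesia. If such use is more frequent in one arm, the difference between arms mixes the drug's effect with that of stimulation. An arm difference is conceivable because site discomfort, one of the triggers in section 5.1, can depend on whether stimulation is active. A participant's arm is the same on both days, so discomfort on the first day could also lead to use on the second.

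The records as described may not resolve this. The medication washout form in section 6.2.2 is completed at the start of the pre-rTMS assessment, so it cannot capture later intake. No clock time relative to the thermal tests is specified elsewhere.

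**Working it through.** **1. The rules side by side, for a dose shortly before stimulation on a scan day**

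| Section | Status of the dose |
|---|---|
| 4.1 | Not compatible: within 24 hours of the post-rTMS scan |
| 5.3.3 | Prohibited: day of the scanner session |
| 5.1, site sensations | Allowed |
| 5.1, headache | Encouraged |
| 5.3.1 | Allowed, subject only to the psychotropic proviso |

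**2. The protocol's own figures on discomfort by arm** (section 7.3, adverse-event table)

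- Site pain: active 59/165 = 35.8%; sham 6/158 = 3.8%. Both reproduce.
- Difference: 0.358 − 0.038 = 0.320.
- Site discomfort: 18/165 = 10.9% against 2/158 = 1.3%.
- If the site-pain rates carried over to 50 per arm: 50 × 0.358 ≈ 18 active and 50 × 0.038 ≈ 2 sham participants.

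The table holds 165 + 158 = 323 people and this trial recruits 100, so it describes another exposure population. Headache is not among the listed terms.

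**3. Size of a bias toward active, if doses fall between baseline and post test**

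Bias (SD of threshold change) = D × u × e × h, where

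- D = arm difference in the share with the trigger: 0 (sham equalises sensation) to 0.320 (section 7.3 table);
- u = share of those who take a drug: assumed, up to 1.0;
- e = drug effect on the threshold change: assumed, up to 0.8 SD;
- h = share of participants whose use can reach the pain day: 1.0, or about 0.5 if only use prompted by an earlier session counts. Prior TMS is excluded, so such use first arises at session two, and day order is counterbalanced (section 9.1).

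| D | u | e | h | Bias (SD) |
|---|---|---|---|---|
| 0 | any | any | any | 0 |
| 0.320 | 1.0 | 0.5 | 0.5 | 0.08 |
| 0.320 | 1.0 | 0.8 | 0.5 | 0.128 |
| 0.320 | 1.0 | 0.8 | 1.0 | 0.256 |

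**4. Effect on a nominal test**

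Take 40 usable participants per arm (section 9.2, stated there for the connectivity outcome; no power calculation is given for pain). The shift in z is bias × √(40/2) = bias × 4.47. The chance of a false result in favour of active is 1 − Φ(1.96 − shift).

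- Bias 0: 0.025.
- Bias 0.08: shift 0.36, giving 0.055.
- Bias 0.128: shift 0.57, giving 0.083.
- Bias 0.256: shift 1.14, giving 0.21.

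**5. Direction**

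Section 5.1 does not say whether a dose before stimulation comes before or after the baseline thermal test. A dose before baseline raises both thresholds. A constant effect cancels in the change, and one that wanes by the post test lowers the change among users. The same dose would also affect the individually set moderate-pain temperature, which is fixed from the baseline test and reused after rTMS (section 6.2.2). The bias toward active is then zero or negative.

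**The case against.** A reader might infer that analgesic use will be more common in the active arm and so will inflate the benefit of active rTMS. The documents do not support that, for these reasons.

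- **Trigger.** The sentence that encourages a drug is tied to headache, which the section 7.3 table does not list. The site-pain figures bear only on the sentence that allows prophylactic use.
- **Population and sham.** The table comes from another exposure population. Here stimulation is at 80% of resting motor threshold, in sessions of about 45 seconds (sections 6.2.4 and 7.4), and the sham uses skin stimulation to imitate the active sensation (section 6.2.3). If that works, the arm difference could be zero.
- **Timing.** Section 5.1 describes use before a session, so use prompted by an earlier session reaches the pain outcome in only about half of participants. Same-day use, for instance in the 15-minute break, is neither described nor ruled out. The table caption says the symptoms occurred only during stimulation.
- **Direction.** A dose before baseline could cancel or reverse the effect.

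All of this stands and limits what can be claimed about bias. The table still makes an arm difference plausible for site sensations, and section 7.4 names pain during stimulation as an expected event.

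The suggestion that drug use would reveal allocation is likewise speculative: the painful sensation would itself be the cue, and the SAP tests the blind.

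Two further defences are weaker. Section 5.3.3 could be read as covering only pain medications that are CNS-active, but section 4.1 has no such limit. Section 9.2 puts more weight on effect sizes than on p-values for the clinical hypothesis, but a bias distorts an effect size just as much.

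**Conclusion.** The contradiction between sections 4.1, 5.1, 5.3.1 and 5.3.3 is real, and the plan cannot be followed as written. It touches the pain-threshold outcome, and no analysis rule covers the use that section 5.1 allows or encourages.

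The consequence is a possible bias of uncertain size and direction. Toward active it ranges from 0 to about 0.26 SD, or to about 0.13 SD if only session-two use in about half of participants matters; with dosing before baseline it could be zero or negative. The upper figures rest on the full 32-point gap carrying over from another population, on every affected participant taking a drug, and on a drug effect of 0.8 SD. The last two are assumptions with no basis in the documents. Without timed intake data the trial could not show where in this range it lies. The point should be addressed, but it is not evidence that the pain result will favour active rTMS.

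**What to change.** 1. Reconcile sections 4.1, 5.1, 5.3.1 and 5.3.3 into one rule on analgesics around scan days. This review does not say which rule.
2. Whatever rule is kept, record the drug and clock time of any analgesic taken on a scan day or the day before, relative to each thermal test, and report use by arm.
3. Keep the as-randomised analysis of all data as the main analysis of the pain outcome.
4. Add one sensitivity analysis with the linear mixed model that section 9.6.1 names for pain (that section also mentions ANOVA, so the model should be specified). Set to missing any pain measurement, baseline or post-rTMS, taken after analgesic intake. Removing only post-rTMS values would leave an affected baseline in place. State that missing at random is an assumption here, because intake may depend on arm and on discomfort.

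The cost is a protocol clarification, a time field on a record already kept on scan days, and one extra analysis with some loss of precision.
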